Thus, we will enroll between 100-200 participants in total. There may be overlap in the Protocol A and Protocol B participants. As previously stated, participants will be given the opportunity (optional) to participate in both Protocols A and B. (Thus, in the event that all participants complete both protocols, we will enroll only 100 total participants, i.e., 50 patients and 50 healthy controls).

This being the first study of its kind, it is difficult to do a formal power and sample size

analysis because we do not have a measure of effect size, but given previous similar studies and our usual rate of loss to follow up, we calculate we will need 50 participants per group for each protocol.

Our enrollment numbers take into account the likelihood of attrition. We will only be able to use data sets that are complete (i.e., data collected from sham, excitatory, and inhibitory TMS). However, we anticipate that a subset of enrolled participants will not be able to complete all three study visits within a protocol because of scheduling or other challenges. Though we aim to enroll up to 50 patients and 50 healthy controls per protocol, we expect that the number of participants on whom we have useable data will be smaller.

Inclusion Criteria:

Patients

- Men and women
- Ages 18-50 years
- Patients diagnosed with schizophrenia (SZ), schizoaffective disorder (SZA), or psychotic bipolar disorder (BP).
- On a stable psychiatric medication regimen for at least a month prior to and during study participation
- Have structural brain MRI data on file from previous participation in research within the McLean Hospital Schizophrenia and Bipolar Disorder Program
- Have clinical diagnostic data (Structured Clinical Interview for DSM-IV: SCID) on file from previous participation in research within the McLean Hospital Schizophrenia and Bipolar Disorder Program

Healthy Controls:

- Men and women
- Ages 18-50 years
- Without major psychiatric illness
- Have structural brain MRI data on file from previous participation in research within the McLean Hospital Schizophrenia and Bipolar Disorder Program

Exclusion Criteria:

Patients

- Any change in psychiatric medications within a month prior to and during study participation
- Legal or mental incompetency
- Intellectual disability
- Substance use disorder (abuse or dependence) with active use within the last 3 months
- Significant medical or neurological illness
- Prior neurosurgical procedure
- History of seizures

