We will test for group differences in demographic and clinical variables using SPSS, using χ^2 and t-tests for ANOVA as appropriate. We will first measure the change (Δ) in each of the pre- and post-TMS assessments at each study visit: i.e. accuracy in time interval discrimination task, accuracy and reaction time (RT) in N-back working memory task, executive function in Flanker task accuracy and RT in repetitive finger tapping task, and accuracy and RT in MSIT. We will then run two-way ANOVA for each outcome measure, with diagnosis (patients vs. healthy controls) and the TMS type (excitatory, inhibitory, or sham) as independent variables. These models will include as covariates sex, age, handedness, medication load, and symptom severities (derived from the clinical scales scores: NAART, PANSS, YMRS, MADRS, PSYRATS, BRIEF-A, BIS-11, and the Fagerstrom Test).

D. Power analysis (e.g. sample size, evaluable subjects)

This is a pilot study. This being the first study of its kind, it is difficult to do a formal power and sample size analysis because we do not have a measure of effect size, but given previous similar studies and our usual rate of loss to follow up, we estimate we will need 50 participants per group for each protocol. Of primary interest to the study is the change (Δ) in outcome measures within the psychosis group. With 50 subjects in the psychosis group, we will have 80% power to detect an effect size of 0.35, which is a moderate effect.

VII. RISKS AND DISCOMFORTS:

Common risks of TMS procedure

Subject may feel twitching of the scalp muscles during stimulation and/or local discomfort (tapping sensation) under the coil. It is possible that the subject may feel a headache after the TMS measurement that is generally caused by keeping the head in the same position for a lengthy period of time and/or by stimulation of the scalp muscles and nerves by the TMS pulses. TMS may also induce nausea in some patients¹¹⁴. The headache or nausea, if present, is typically mild, disappears soon and can be treated by mild over-the-counter analgesics.

Although there are no reports suggesting increased risk for TMS during pregnancy, pregnant women are excluded from this study due to insufficient knowledge of the effects of the strong magnetic fields on the fetus.

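### Protocol VI.D states 80% power for the 50 patients to be enrolled, although Section III expects fewer than 50 usable data sets

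*Protocol*

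**What the plan says.** The power claim is in Protocol Section VI.D, under the heading "D. Power analysis (e.g. sample size, evaluable subjects)". It reads: "With 50 subjects in the psychosis group, we will have 80% power to detect an effect size of 0.35, which is a moderate effect". Just before it, the section gives the origin of the 50: previous similar studies and "our usual rate of loss to follow up, we estimate we will need 50 participants per group for each protocol". It then indicates what the power refers to: "Of primary interest to the study is the change" in outcome measures among patients.

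Protocol Section III treats the same 50 as the enrolment target:

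- The target: "we aim to enroll up to 50 patients and 50 healthy controls per protocol".
- The attrition allowance: "Our enrollment numbers take into account the likelihood of attrition".
- The analysis rule: "We will only be able to use data sets that are complete (i.e., data collected from sham, excitatory, and inhibitory TMS)".
- The expected result: "we expect that the number of participants on whom we have useable data will be smaller".

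The Compensation part of Section V also says that data from all three visits are needed.

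No attrition rate or evaluable number appears anywhere. VI.D names no test, contrast or effect-size metric, and neither document states an alpha or sidedness. The SAP contains no power statement.

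**The concern.** An enrolment number that allows for dropout should exceed the number on which power is calculated. Here one figure does both jobs. Fifty is what remains to be eroded by attrition, and it is also the number to which 80% power is attached. Since Section III limits use to complete three-visit sets and expects fewer than 50, the power figure belongs to a sample the plan does not expect to have.

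What is at stake is how a null result would be read. VI.D holds the only quantified statement of sensitivity in either document. A reader would take it that an effect of 0.35 had an 80% chance of detection among the patients analysed. Without the metric, alpha and sidedness, that reader also cannot tell which effect is meant.

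**Working it through.** **Inputs from the documents.** Effect size 0.35, power 80% and n = 50 patients (VI.D). Fifty patients enrolled per protocol, usable number smaller and not given (Section III).

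**Assumptions, none of them in the documents.** Effect size as a standardised within-patient change d (mean change divided by the SD of the change). This is the natural reading, because VI.D has just named change within the patient group. Paired or one-sample t-test at alpha 5%, one- and two-sided. Completers of 45 (10% loss) and 40 (20% loss).

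**Step 1: reproduce the stated figure at n = 50.** With the normal approximation, power = Φ(d√n − z), and d√n = 0.35 × √50 = 2.475.

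- One-sided 5%: Φ(2.475 − 1.645) = Φ(0.830) = 79.7%. The exact noncentral t with 49 degrees of freedom gives 78.7%.
- Two-sided 5%: Φ(2.475 − 1.960) = Φ(0.515) = 69.7%. The exact figure is 68.0%.

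On this reading the stated 80% is recovered, within rounding, by a one-sided 5% test with all 50 patients complete. It is not recovered by a two-sided 5% test.

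**Step 2: replace 50 by fewer completers.** Power is the exact noncentral t at d = 0.35. The detectable effect is the d at which that power equals 80%.

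| Complete patients | Power, one-sided 5% | Power, two-sided 5% | Detectable d, one-sided | Detectable d, two-sided |
|---|---|---|---|---|
| 50 | 78.7% | 68.0% | 0.36 | 0.40 |
| 45 (assumed) | 74.8% | 63.2% | 0.38 | 0.43 |
| 40 (assumed) | 70.2% | 57.9% | 0.40 | 0.45 |

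From 50 to 40 completers, power falls by 78.7 − 70.2 = 8.5 points one-sided and 68.0 − 57.9 = 10.1 points two-sided.

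**Step 3: does the shortfall depend on the metric?** It does.

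- *Three-condition repeated-measures F.* Take f = 0.35 in the partial-eta convention, sphericity, 2 and 2(n − 1) degrees of freedom, and noncentrality f² × 2(n − 1). At n = 50 the noncentrality is 0.1225 × 98 = 12.0. Power is 87.3% at 50, 83.2% at 45, 80.2% at 42 and 78.0% at 40.
- *Raw-score SD units.* With pre/post correlation ρ, d becomes 0.35/√(2(1 − ρ)). Two-sided 80% then needs ρ = 0.625 at n = 50 or ρ = 0.703 at n = 40.

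Some unstated metrics therefore absorb a degree of loss and stay at 80%.

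**The case against.** The strongest reply is that nothing in VI.D has been shown to be miscalculated. The sentence is conditional on 50 subjects, and 80% is recovered under a one-sided test. The hypotheses in Section II are directional, so a one-sided calculation is plausible. This stands. A reader might infer that the 80% is an arithmetic error, and the documents do not support that.

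A reader might also infer that the study will fall short of 80% power whatever was meant. That is not supported either. With the repeated-measures F in Step 3, power stays at or above 80% down to about 42 completers, and a high enough pre/post correlation does the same in raw-score units. The 8.5- and 10.1-point falls belong to the paired reading and to completer numbers assumed here.

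The consequence is also modest. VI.D calls the study a pilot and says a formal calculation is difficult, VI.B names no endpoint, and the 50 is attributed to earlier studies and usual losses, not derived from 0.35. Section III openly says usable data will be fewer. That lowers the severity, but the same disclosure creates the inconsistency, because VI.D does not carry it through.

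Finally, the SAP's mixed models could in principle use patients with incomplete visits, which would soften the loss. The SAP does not say so, and Section III says the opposite. Which rule governs the analysis set is a separate question and is not pressed here.

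**Conclusion.** The point holds as an inconsistency of low severity in the stated power. The 80% is attached to the enrolment target, while Section III expects to analyse fewer patients. That conclusion rests on the text alone and needs no assumption about the test or metric.

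The size does need assumptions. For a standardised within-patient change tested at 5%, 80% requires an undeclared one-sided test and no losses. Two-sided power is 68% even with all 50 complete. At an assumed 40 completers it is 70% one-sided or 58% two-sided. The missing alpha, sidedness and metric make the claim impossible to verify, but do not by themselves show it to be wrong.

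**What to change.** Keep enrolment as it is. Restate VI.D on the expected number of evaluable patients, give the loss assumed, and name the contrast, effect-size metric, test, alpha and sidedness.

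If a standardised within-patient change at two-sided 5% is meant, the sentence could say that 80% power is available for an effect of 0.40 with 50 complete patients, 0.43 with 45 and 0.45 with 40, with the chosen loss stated. If a one-sided 5% test is intended and declared, the figures are 0.36, 0.38 and 0.40. If another metric was used, state it with the correlation or sphericity assumed. These figures are illustrative: they approximate a mixed-model contrast, are not adjusted for multiple outcomes, and do not apply to the Friedman test planned for the symptom scales.

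The cost is two or three sentences in VI.D, and one in the SAP if a one-sided test is declared. No patients are added and the design is unchanged. The downside is a slightly less favourable stated sensitivity and an attrition assumption put in writing.

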The cerebellum plays a major role in information processing but it has not been considered a treatment target for studies of major mental illness. The goal of this study is to investigate the impact of modulating cerebellar activity on mood and psychotic symptoms in patients as well as the closely related domains of executive function and time perception. We will study up to 100 healthy subjects and up to 100 psychosis patients (i.e., schizophrenia, schizoaffective disorder, and psychotic bipolar disorder). In sham-controlled crossover design, we will present validated cognitive paradigms and clinical measures to subjects before and after TMS. We hypothesize that abnormally reduced activity in the cerebellum contributes to the abnormalities in patients and therefore cerebellar stimulation will normalize outcome measures. The circuitry of the cerebellum is complex and the main projection neurons in this brain region (Purkinje cells) are inhibitory. Therefore, we will test the specificity of our hypothesis by including an "inhibition" TMS condition which we hypothesize will worsen the outcome measures. The specific aims are to:

Aim 1: Investigate the role of the cerebellum in abnormalities of time perception, cognition, and mood and psychotic symptoms by evaluating these functions before and immediately after excitatory, inhibitory, or sham TMS applied to the cerebellum in patients with psychosis and in healthy control participants. Participants will undergo three study visits, one for each of the three TMS conditions. At each study visit, we will measure the following before and after TMS:

- a) **Time perception:** We will measure time perception using a time perception task. *Hypothesis:* Compared with healthy control participants, patients with psychotic disorders will have impaired timing perception (i.e., higher number of errors and/or greater inter-trial variability in the task) both at baseline and after sham TMS. We predict that the abnormalities in patients will further worsen after inhibitory TMS, and improve after excitatory TMS.

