PROTOCOL TITLE

Cerebellar transcranial magnetic stimulation (TMS) in psychotic disorders: effect on time perception, executive function, and mood and psychotic symptoms

NCT Number: NCT02642029

Date: August 22, 2022

Statistical Analyses:

We will test for group differences in demographic and clinical variables using χ^2 and t-tests or ANOVA, as appropriate. To examine the effect of TBS conditions on symptoms (as measured by visual analog scale scores, which are not normally distributed), we will conduct the non-parametric Friedman's test. For all other outcome measures, we will use mixed model regressions with TMS condition (cTBS, iTBS, or sham TBS), time (pre-TMS, post-TMS), and the interaction of condition x time as the primary variables of interest. To test the association between performance on the interval discrimination task (IDT) and symptoms, we will run mixed model regression models with TMS condition and time in addition to symptom score as the primary variable of interest.

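### The 80% power in VI.D is for an uncontrolled change within patients; no power is given for the comparison of that change between cTBS, iTBS and sham, which is what the planned analyses test

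*Protocol*

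**What the plan says.** Protocol section VI.C defines the quantity: "We will first measure the change (Δ) in each of the pre- and post-TMS assessments at each study visit". Each visit delivers one TMS condition, so Δ is a change within one condition. The same section then compares Δ across conditions: "We will then run two-way ANOVA for each outcome measure, with diagnosis (patients vs. healthy controls) and the TMS type (excitatory, inhibitory, or sham) as" the two factors.

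Section VI.D says "Of primary interest to the study is the change (Δ) in outcome measures within the psychosis group", and follows with "With 50 subjects in the psychosis group, we will have 80% power to detect an effect size of 0.35". It names no sham contrast, test, alpha, sidedness, standard deviation or correlation.

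The design is comparative. Section II says "In sham-controlled crossover design, we will present validated cognitive paradigms and clinical measures to subjects before and after TMS". For every outcome except the visual analogue scales, the SAP specifies mixed models with condition, time and "the interaction of condition x time as the primary variables of interest". The interaction asks whether Δ differs between cTBS, iTBS and sham. The visual analogue scales go to Friedman's test. Neither document gives power for any comparison between conditions.

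**The concern.** A change from before to after stimulation at one visit contains more than a stimulation effect. Tasks repeated within a visit and over three visits can shift through practice or fatigue. The protocol itself plans to ask subjects which mode they think they received, in order to assess expectation. The sham condition is there to remove these components, so power to detect a non-zero Δ is not power to detect an effect of TMS.

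The two quantities also differ in precision. A difference between two changes has its own standard deviation, which may be larger or smaller than that of one change, depending on how strongly the changes correlate within a patient. A reader who takes the 80% as sensitivity to a sham-controlled effect could misjudge what a null comparison means.

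**Working it through.** **Inputs.** From the protocol: n = 50 patients, effect size 0.35, stated power 80%, and the definition of Δ. From the SAP: a condition-by-time interaction with three conditions and two times. Assumed, because the documents are silent: alpha 0.05, with both one- and two-sided tests tried, and rho, the correlation of Δ between visits in the same patient, shown from 0 to 0.75. Δ is taken to have the same SD in each condition.

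**Step 1: reproduce the stated figure.** One-sample t-test of Δ, noncentral t with 49 df and noncentrality 0.35 × √50 = 2.47:
- one-sided 5%: 78.7% (79.7% by the normal approximation), which matches the stated 80%;
- two-sided 5%: 67.9% (69.7%), which does not.

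With n = 50, the effect detectable with 80% power is 0.357 one-sided and 0.404 two-sided. Other readings fit poorly: two groups of 50 give 54% one-sided and 42% two-sided, and a repeated-measures ANOVA with f = 0.35 gives 97% or more. A correlation of 0.35 with n = 50 gives 80.5% one-sided, but VI.D describes a change, not a correlation.

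**Step 2: one active-minus-sham difference in Δ.** SD(difference) = SD(Δ) × √(2(1 − rho)). A difference of 0.35 SD(Δ) therefore has standardised size d = 0.35 / √(2(1 − rho)). The last column is 0.404 × √(2(1 − rho)).

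| rho | √(2(1 − rho)) | d | Power, two-sided | Power, one-sided | Difference detectable with 80% power, two-sided, in SD(Δ) |
|---|---|---|---|---|---|
| 0 | 1.414 | 0.247 | 40% | 53% | 0.57 |
| 0.3 | 1.183 | 0.296 | 54% | 66% | 0.48 |
| 0.5 | 1.000 | 0.350 | 68% | 79% | 0.40 |
| 0.75 | 0.707 | 0.495 | 93% | 96% | 0.29 |

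At rho = 0.5 the sham-controlled contrast has exactly the power of the uncontrolled test; above 0.5 it has more.

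**Step 3: the SAP's own test.** With three conditions the interaction has 2 df. Noncentrality = 50 × SS / (1 − rho), where SS is the sum of squared deviations of the three mean changes (in SD of Δ) from their average; F has 2 and 98 df.
- Only one active condition shifts, means (0.35, 0, 0): SS = 0.0817. At rho = 0 the noncentrality is 4.08 and power 41%. At rho = 0.5 power is 71%.
- The active conditions shift in opposite directions, means (0.35, −0.35, 0): SS = 0.245. At rho = 0 the noncentrality is 12.25 and power 88%.

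**The case against.** The strongest objection is that the SAP's test is not one pairwise contrast. It has 2 df, and the protocol predicts that excitatory TMS improves and inhibitory TMS worsens performance in patients. Under that pattern at 0.35 SD each way, the interaction test has about 88% power even at rho = 0. This stands. A reader might infer from the 40% to 53% that the trial is underpowered for its planned test; the documents do not support that. Those figures belong to a single active-versus-sham contrast with uncorrelated changes, and no value of rho is documented.

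A reader might also set the stated 80% against 40%. That mixes two issues. Like for like, the fall at rho = 0 is from 79% to 53% one-sided, or from 68% to 40% two-sided.

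Third, 0.35 could have been meant as a standardised difference in Δ between conditions, since VI.C analyses Δ by TMS type. The text does not say so; it ties the figure to the change within the psychosis group. Even on that reading, power would be 68% two-sided, and 79% only one-sided.

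Finally, the protocol calls this a pilot study and says a formal power analysis is difficult without an effect size. That limits how much weight the figure carries. VI.D nevertheless makes a numerical claim, and the claim should concern the comparison that is planned.

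**Conclusion.** The point holds as a mismatch between the quantity powered and the quantity tested. The 80% is reproduced as an uncontrolled, one-sided, one-sample test of Δ, and the sham-controlled comparison has no stated power.

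The consequence depends on two things the documents leave open. One is rho: for a single active-versus-sham contrast, two-sided power runs from 40% at rho = 0 to 93% at rho = 0.75, with no loss at 0.5. The other is the pattern of effects: at rho = 0 the 2-df test has about 41% power if one active condition works and about 88% if both shift as hypothesised.

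All these figures assume 50 patients with complete data and alpha 0.05. Protocol section III expects fewer usable patients, which would lower them. They concern the task outcomes only, not the visual analogue scales.

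**What to change.** Restate VI.D for the sham-controlled comparison. For example: with 50 evaluable patients and a two-sided 5% level, there is 80% power for an active-minus-sham difference in Δ of 0.40 SD of that difference, equal to 0.57, 0.48, 0.40 and 0.29 SD of Δ at assumed correlations of 0, 0.3, 0.5 and 0.75.

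Add the power of the 2-df condition-by-time test under the hypothesised pattern, with its assumed rho. Label 0.35 as a one-sided, uncontrolled within-condition figure, or remove it. Say that the calculation covers the task outcomes and not the visual analogue scale scores tested by Friedman's test.

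The cost is a few lines of text and, for a single active-versus-sham contrast at low rho, a less favourable figure. No more patients are needed and the design does not change.

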PROTOCOL TITLE

Cerebellar transcranial magnetic stimulation (TMS) in psychotic disorders: effect on time perception, executive function, and mood and psychotic symptoms

NCT Number: NCT02642029

Date: August 22, 2022

Statistical Analyses:

We will test for group differences in demographic and clinical variables using χ^2 and t-tests or ANOVA, as appropriate. To examine the effect of TBS conditions on symptoms (as measured by visual analog scale scores, which are not normally distributed), we will conduct the non-parametric Friedman's test. For all other outcome measures, we will use mixed model regressions with TMS condition (cTBS, iTBS, or sham TBS), time (pre-TMS, post-TMS), and the interaction of condition x time as the primary variables of interest. To test the association between performance on the interval discrimination task (IDT) and symptoms, we will run mixed model regression models with TMS condition and time in addition to symptom score as the primary variable of interest.

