As part of the clinical evaluation, we will also ask female participants about and record the first date of their last menstrual period (LMP). Clinical symptoms and cognitive functioning can vary according to the phase of the menstrual period. We will evaluate what phase of the menstrual cycle a female participant is in at the time of each study visit so that we can potentially control for any associated confounding effects.

Similarly, nicotine is well-documented to affect cognitive functioning, and is an important variable to control for. Therefore, we will administer a Fagerstrom Test for Nicotine Dependence in all research participants. For individuals who are smokers, we will record the time of the participant's last cigarette prior to each study visit.

For all subjects, during each and every visit, urine toxicology screens will be used to assess for current substance use, and urine pregnancy tests in women of child-bearing age to determine if she is

pregnant (and thus is ineligible to participate in the study).

Scheduling of study visits

As mentioned before, this will be a cross-over design, in which participants will undergo excitatory, inhibitory, and sham TBS over three study visits, separated by at least 36 hours. The order in which participants receive excitatory vs. inhibitory vs. sham TMS will be randomized.

The effects of a single session of rTMS are acute and reversible, and usually recede in less than an hour. Nonetheless, the study visits will be separated by at least 36 hours in order to provide more than ample time for the brain to return to homeostatic balance and ensure that there are no potential residual TMS effects from the previous study visit.

If scheduling permits, participants may be able to complete all three study visits in as short as one week. However, to accommodate scheduling flexibility for research participants, we will allow up to two months for participants to complete all three study visits within a single protocol.

Participants will participate in one of two protocols, Protocol A (**Figure 2**) or Protocol B (**Figure 3**). The two protocols are identical except that they involve different time perception and executive function tasks. Specifically, the tasks in Protocol A are the interval discrimination task, flanker task and the N-back working memory task, while those in Protocol B are the repetitive finger tapping task and the multi-source interference task (MSIT).

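### The task-outcome models use each visit's pre-TMS score only by subtraction; adjusting for it would make the TMS contrasts more precise at no data cost

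*SAP*

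**What the plan says.** Each task is performed before and after TMS at all three visits (Protocol V, Summary of Study Procedures). Protocol VI.C states: "We will first measure the change (Δ) in each of the pre- and post-TMS assessments at each study visit". It then runs a two-way ANOVA of that change on diagnosis and TMS type. On covariates it says: "These models will include as covariates sex, age, handedness, medication load, and symptom severities", the severities coming from the clinical scales. The visit's own pre-TMS task score is not listed.

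The SAP moves to raw scores: "we will use mixed model regressions with TMS condition (cTBS, iTBS, or sham TBS), time (pre-TMS, post-TMS), and the interaction of condition x time". It names no baseline covariate, no constraint on the pre-TMS means and no covariance structure. The visual analogue scales go to Friedman's test and are outside this point.

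Three other statements bear on it. Order of TMS type is randomised for each participant (Protocol IV, Treatment assignment, and randomization). Visits are at least 36 hours apart to "ensure that there are no potential residual TMS effects from the previous study visit" (Protocol V, Scheduling of study visits). Protocol VI.D says: "Of primary interest to the study is the change (Δ) in outcome measures within the psychosis group".

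**The concern.** A single pre-TMS task score carries measurement error. Subtracting it passes all of that error into every TMS contrast. When the conditions share the same expected pre-TMS mean, as they do here by randomised order and the assumed absence of residual effects, the efficient coefficient on the pre-TMS score is rho_w rather than 1. Here rho_w is the correlation of pre and post scores across visits within a person, after stable person differences are removed.

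The covariates in Protocol VI.C do not help. They describe the participant (the scales are given only at the first visit) and so do not alter a within-person comparison of TMS types. Adding a visit-level random effect to the SAP model does not remove the loss either, because each condition still has its own free pre-TMS mean. What is at stake is wider intervals and a greater chance of missing a real effect of iTBS or cTBS.

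**Working it through.** **Inputs.** n = 50 patients, effect size 0.35, power 80% (Protocol VI.D). Alpha, sidedness and the SD behind 0.35 are not stated; I take alpha 0.05 and a paired d on the change contrast. rho_w is not given, so a range is shown.

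**Reproducing the stated power.** Protocol VI.D: "With 50 subjects in the psychosis group, we will have 80% power to detect an effect size of 0.35". For a paired test with n = 50 and d = 0.35:
- One-sided 5%: 79.7% (normal) or 78.7% (noncentral t). This reproduces 80%.
- Two-sided 5%: 69.7% (normal) or 67.9% (noncentral t). This does not.

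Both are carried forward.

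**What the SAP interaction estimates.** In a random-intercept fit to simulated complete data (50 people, three visits), the condition x time coefficient was 0.0835 and the difference in mean change was 0.0835. The model standard error was 0.2593, equal to sqrt(4 x residual variance / 50). The model subtracts the pre-TMS score and does nothing more with it.

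**Variance per participant of an active-versus-sham contrast**, with within-person variance s²:
- Change score or condition x time: two visits, each 2s²(1 − rho_w), total 4s²(1 − rho_w).
- Adjusted for the pre-TMS score: two visits, each s²(1 − rho_w²), total 2s²(1 − rho_w²).
- Ratio: 2(1 − rho_w²) / [4(1 − rho_w)] = (1 + rho_w)/2.

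The adjusted power uses d = 0.35 / sqrt(ratio); for example, at rho_w 0.5, 0.35 / sqrt(0.75) = 0.404.

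| rho_w | variance ratio | n giving the precision of 50 unadjusted | power, two-sided (from 67.9%) | power, one-sided (from 78.7%) |
|---|---|---|---|---|
| 0 | 0.50 | 25 | 92.9% | 96.5% |
| 0.3 | 0.65 | 32.5 | 85.3% | 91.7% |
| 0.5 | 0.75 | 37.5 | 80.0% | 88.0% |
| 0.7 | 0.85 | 42.5 | 74.9% | 84.2% |
| 0.8 | 0.90 | 45 | 72.5% | 82.3% |
| 0.9 | 0.95 | 47.5 | 70.2% | 80.5% |

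(Noncentral t.) If 0.35 instead refers to the change at one visit, with independent visits, the paired d is 0.35/sqrt(2) = 0.247. Two-sided power then goes from 40% to 57%, 51%, 46% and 42% at rho_w 0.3, 0.5, 0.7 and 0.9.

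**Simulation check** (50 participants, six balanced orders, period effects modelled, 4,000 runs). Variance ratios were 0.504, 0.584, 0.757 and 0.914 at rho_w 0, 0.2, 0.5 and 0.8, against 0.50, 0.60, 0.75 and 0.90 in theory. In a separate run of 4,000 trials per setting, type I error of the adjusted analysis was 0.049 to 0.056, with no bias.

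**Two conditions on the gain.**
- Visit number must be in the model. Change scores cancel an additive practice shift; a coefficient below 1 does not. With practice effects and no visit term, the simulated ratio at rho_w 0.5 was 0.82 instead of 0.75; including the term restored it.
- Carry-over must be absent. With an imposed persistent carry-over of 0.3 within-person SD at rho_w 0.5, the adjusted estimate had bias of about 0.05 SD and type I error of 0.068. The change score stayed unbiased.

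**The case against.** The strongest reply is that nothing planned is wrong. The change contrast is valid, does not need equal pre-TMS means across conditions, and is robust to carry-over of the kind simulated. Change is also what the protocol declares to be of primary interest. The study calls itself a pilot, concedes that "it is difficult to do a formal power and sample size analysis because we do not have a measure of effect size", and gives no correlation from which the benefit could be sized. All of that stands. It makes this an efficiency improvement and argues for a fix that still reports change.

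A careless adjustment could also do harm. The protocol's aims predict that patients are worse than controls at baseline and after sham. Entering the participant's mean pre-TMS score as a covariate adjusts that difference away: in a simulation with a baseline gap of 0.8 and no group difference in change, the post-TMS patient-control difference shrank from −0.82 to −0.21. This stands too, and it shapes the fix.

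A reader might infer that the pre-TMS score is the only covariate recorded visit by visit, so that nothing else could sharpen the contrasts. Protocol V (Clinical characterization) shows otherwise: time of last cigarette and menstrual phase are also established for each visit.

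**Conclusion.** The point holds as a loss of precision in the TMS contrasts for the task outcomes. The variance ratio (1 + rho_w)/2 rests on randomised order, no carry-over into the next visit's pre-TMS score, equal pre and post variances, and visit number in the model. The real loss is unknown because rho_w is not given. At rho_w 0.5 it is a quarter of the precision, worth about 12 points of power two-sided or 9 one-sided at n = 50 and d = 0.35. Above about 0.8 the gain is under 5 points on either basis.

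Three stronger readings are not supported:
- That the planned analysis is biased or invalid. It is neither.
- That half the precision is lost. For non-negative rho_w that is only the limit at rho_w = 0, and no document puts rho_w there.
- That this point shows true power to be 68% rather than 80%. The gap reflects unstated sidedness, which is a separate matter; the gain from adjustment exists on either basis.

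**What to change.** In the SAP, for task outcomes only:

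- Keep the pre/post mixed model, which still yields the within-condition change. Specify a participant random effect, a visit-within-participant random effect and a visit-number term.
- Constrain the pre-TMS mean to be common to the three TMS conditions: drop the condition main effect and keep time and condition x time.
- When patients and controls are modelled together, let the pre-TMS mean differ by diagnosis, so that the hypothesised baseline and post-sham group differences are preserved.
- Report the unconstrained condition x time (change-score) result as a sensitivity analysis, because the constrained model relies on no carry-over.

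An alternative for the TMS contrasts alone is a model of the post-TMS score on condition and visit number, with the participant-centred pre-TMS score as covariate. The participant-mean pre-TMS score should not be entered when the diagnosis main effect is estimated.

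The cost is a few lines of SAP wording and one re-specified model, with no new data or visits. The downside is dependence on the no-carry-over assumption, which the protocol already makes and which the sensitivity analysis guards.
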